- 2. A four to five hour timeframe from the onset of symptoms to administration of standard of care attack treatment in the current study is less than the delay in treatment observed in pivotal studies of acute attack medications in which treatments were found to be efficacious. For instance, in the FAST-3 study of icatibant, the mean (SD) time from onset of symptoms to blinded study drug treatment in 43 subjects was 7.07 (3.17) hours; in FAST-3, icatibant-treated attacks had a median time to onset of symptom relief of 2 hours (Lumry, Li et al. 2011).
- 3. After administration of study drug, subjects may treat an attack with their standard of care attack medication before 4 hours post administration of study drug, if they feel that the attack symptoms warrant earlier treatment.

Exclusion of approved kallikrein inhibitor attack prophylaxis with C1 INH is required to clearly demonstrate proof of concept of BCX7353. Additionally, use of androgens is prohibited due to possible interference of androgen metabolism by CYP3A4 from the inhibitory effect of BCX7353, resulting in higher androgen concentrations (see Section 9.7.1).

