- 4. The subject will call the on-call study Investigator (or designee) at least 4 hours after taking study medication (or earlier if they have any concerns over the course of their symptoms) to review their response to study drug and diary completion. The on-call study Investigator (or designee) will call the subject if they have not heard from the subject within 5 hours of their initial phone call. Subjects who did not require standard of care at 4 hours will be reminded at the telephone call, by the Investigator, that they may use standard of care at any time point at their own discretion if not experiencing improvement or if they are experiencing progression of the HAE attack. An exception to the requirement of a phone call follow-up at 4 hours may be made if the 4 hour timepoint occurs during the typical period of sleep and the subject is asleep at 4 hours post-study medication. In this case, the subject will be required to call the on-call Investigator (or designee) upon waking.

Subjects will complete a diary questionnaire and a 3-component VAS on a 100 mm scale for abdominal pain, cutaneous pain, and cutaneous swelling immediately prior to study drug administration and at 1, 2, 3, 4, approximately 8 and at 24 hours after study drug administration. Subjects sleeping during these timepoints (see #4 exception above) will be required to complete the diary questionnaire upon waking. Subjects will also be asked to track the start and stop times of any attacks not treated with study drug that occur after the baseline visit through the last study visit (Post-Attack 3 visit).

At each clinic visit following treatment of an attack with study drug, the diary will be reviewed. Any re-education required to ensure correct diary completion will be performed and safety assessments will be completed. At Post-Attack 1 and Post-Attack 2 clinic visits, the subject will be dispensed their next randomized dose of study drug and a new attack diary. Completed diaries will be collected at each visit to avoid subjects referencing back to previous attack entries.

Each subject will continue on study to treat 3 protocol-qualifying attacks with study drug. Clinic visits will be scheduled 10 to 14 days after each attack that is treated with study drug. Any additional attacks that occur in the intervening periods between study visits may be treated according to standard of care for the subject.

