## 7.2. Endpoints

# 7.2.1. Efficacy Endpoints

The efficacy endpoints of this study are as follows:

- Proportion of subject attacks with an improved or stable 3-symptom composite VAS score at 4 hours post-dose. The 3-symptom composite will be calculated as the average of the VAS scores for abdominal pain, skin pain, and skin swelling. A subject is considered improved or stable if the change from baseline (time of drug administration) in VAS is less than or equal to 0
- Proportion of subject attacks with a patient global assessment of improved or stable symptoms at 4 hours post-dose
- Proportion of subject attacks with no symptoms or mild symptoms of an HAE attack at 4 hours post-dose
- Proportion of subject attacks requiring standard of care attack treatment through 24 hours post-dose
- Time to use of standard of care acute attack treatment through 24 hours post-dose
- Time to stable or improved symptoms by composite VAS score through 24 hours post-dose
- Time to symptom relief (first documented time point when a subject experiences a 50% reduction in the 3-symptom composite VAS from the pretreatment composite score)
- Time to almost complete symptom relief (first documented time point when a subject records a VAS score < 10 mm in the 3-symptom composite VAS score)
- Time to initial symptom relief (time from ingestion of study medication to report that the worst symptoms of the attack are over)
- Time to complete symptom relief (time from ingestion of study medication to no HAE attack symptoms)

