# 13.3.3. Analysis of Efficacy Variables

As this is the first study of BCX7353 in the treatment of acute attacks, the analysis of attack resolution will be described in a number of ways which will be fully detailed in the SAP. The endpoint that may be utilized to first examine efficacy is the proportion of subject attacks with a stable or improved VAS at 4 hours postdose in the full analysis set. The number and proportion of subject attacks with a stable or improved VAS at 4 hours postdose will be summarized by treatment group. Attacks that require standard of care medication prior to the 4 hour time point will be considered as failure (i.e., not having a stable or improved VAS at 4 hours postdose). To assess treatment differences, a logistic mixed effect model including treatment, period and sequence as fixed effects, and subject within sequence as a random effect will be utilized. Other binary endpoints will be analyzed in a similar manner.

The 3-symptom composite VAS and its associated changes from baseline will be summarized for each attack by time point and treatment group. Treatment differences in the change from baseline values at each time point will be assessed with a mixed effect linear model with factors for treatment, period, sequence, and baseline value as fixed effects, and subject within sequence as a random effect. Analyses of other continuous variables will be analyzed in a similar manner.

The time to use of standard of care medication will be estimated using the method of Kaplan-Meier. For each attack, subjects who do not use standard of care medication will be censored at the end of the attack observation period (i.e., 24 hours). Treatment differences will be assessed using an appropriate proportional hazards model. Analyses of other type to event variables will be analyzed in a similar manner.

Location of attacks, duration of attacks, and number of acute HAE medications administered will be summarized for each treatment group.

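### Protocol 202 gives no rule for standard-of-care use in its five time-to-relief endpoints or its VAS change models, so relief after rescue counts for the blinded treatment and would attenuate a real drug effect

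*Protocol*

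**What the plan says.** - **Endpoints (Protocol 7.2.1).** Five of the ten efficacy endpoints are times to relief: stable or improved VAS, symptom relief, almost complete relief, initial relief and complete relief. Symptom relief is the "first documented time point when a subject experiences a 50% reduction in the 3-symptom composite VAS from the pretreatment composite score". None of the five mentions SoC.
- **Rescue rule (Protocol 13.3.3).** For the 4-hour VAS responder endpoint: "Attacks that require standard of care medication prior to the 4 hour time point will be considered as failure". The extension is "Other binary endpoints will be analyzed in a similar manner".
- **Time-to-event analysis (13.3.3).** For time to SoC, "subjects who do not use standard of care medication will be censored at the end of the attack observation period (i.e., 24 hours"). For the rest: "Analyses of other type to event variables will be analyzed in a similar manner". No other censoring or rescue rule is given.
- **VAS change (13.3.3).** "Treatment differences in the change from baseline values at each time point will be assessed with a mixed effect linear model". The model has no rescue term and no exclusion of values after SoC.
- **When SoC may be taken (7.1.2).** From 4 hours if the attack is not improving or is progressing, and before 4 hours if it progresses rapidly or intraoral symptoms develop. Subjects who did not need it at 4 hours are reminded by phone that, if the attack is not improving or is progressing, "they may use standard of care at any time point at their own discretion".
- **Diary (7.1.2, 11.2.2.1).** VAS is recorded before dosing and at 1, 2, 3, 4, about 8 and 24 hours. Medication use is recorded through 24 hours.
- **Deferral (13.3, 13.3.3).** Details are left to a SAP for this study. The SAP supplied is for Study BCX7353-302, a prophylaxis trial, and has no rule for these endpoints.

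**The concern.** SoC is offered to attacks that are failing on the blinded dose, and it is effective treatment. If relief after SoC counts as the event, a failed attack that is rescued soon after 4 hours and is relieved by the 8-hour entry becomes a relief event at 8 hours for the treatment that failed.

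If BCX7353 works, placebo attacks should fail, and be rescued, more often. They then receive more of this credit, and the contrast moves toward no difference. The protocol recognises the mechanism: section 5.4.3.1 justifies asking subjects to wait 4 hours for SoC because the wait is needed to show an effect against placebo. That protection ends at 4 hours, while the relief endpoints and the VAS models continue to 24.

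The stake is how well this study informs later ones. Section 7.1.1 foresees using the data for planning, and Parts 2 and 3 have at most 12 subjects each, which leaves little room for a diluted contrast.

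**Working it through.** The protocol gives no effect size, event count or power for Study 202, so there is no planned figure to reproduce.

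**Step 1. Which analyses have a rescue rule**

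| Analysis | Rule for SoC in 13.3.3 |
|---|---|
| 4-hour VAS responder | SoC before 4 h is failure |
| Other binary endpoints | Handled similarly |
| Proportion using SoC; time to SoC | SoC is the outcome |
| Five time-to-relief endpoints | None; the only censoring described is at 24 h |
| VAS change at 1, 2, 3, 4, about 8 and 24 h | None |

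Because SoC is allowed before 4 hours, VAS change at 1 to 4 hours has the same gap as at 8 and 24 hours.

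**Step 2. How soon rescue relief reaches the diary.** Section 5.4.3.1 reports that "icatibant-treated attacks had a median time to onset of symptom relief of 2 hours". Assume exponential relief times with that median, and SoC taken at 4 hours. The probability of relief by hour t is 1 − 0.5^((t − 4)/2):

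- 8 h: 1 − 0.5^2 = 0.75
- 24 h: 1 − 0.5^10 = 0.999

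Most rescued attacks would show relief at the next diary entry.

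**Step 3. Effect on 24-hour proportions.** Recorded relief = relief without rescue + proportion rescued × relief after rescue. All inputs are assumptions.

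- Relief without rescue 15% placebo, 45% active (30 points); rescued 60% and 30%; 70% relieved after rescue: 15 + 0.60 × 70 = 57% and 45 + 0.30 × 70 = 66%, a difference of 9 points.
- Same, with 90% relieved after rescue: 69% and 72%, a difference of 3 points.
- With rescue also at 40% and 20%, and at 70% and 40%, the difference ranges from 3 to 16 points.
- Relief without rescue 25% and 50% (25 points), same grid: −2 to 11 points.

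**Step 4. Effect on the planned metric, a hazard ratio.** Simulation of 20,000 placebo and 40,000 active attacks (the 1:2 ratio of the design). Relief times are exponential, at 0.02 vs 0.08 per hour (true HR 4.0), 0.03 vs 0.06 (2.0) or 0.02 in both arms (1.0). SoC is taken at 4 hours plus an exponential delay of mean 2 hours, only in attacks not yet relieved. Relief after SoC has a 2-hour median. Times are rounded up to the diary points and a Cox model is fitted. Within-subject correlation and SoC before 4 hours are ignored. P is placebo, A is active.

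| True HR | Rescued P / A | Relief by 24 h, no rescue, P / A | Relief by 24 h, as written, P / A | HR as written | HR, SoC = not relieved | HR, censored at SoC |
|---|---|---|---|---|---|---|
| 4.0 | 71% / 31% | 38% / 86% | 87% / 93% | 1.36 | 5.24 | 3.67 |
| 4.0 | 53% / 19% | 38% / 85% | 75% / 90% | 1.66 | 4.87 | 3.76 |
| 4.0 | 45% / 25% | 38% / 85% | 69% / 91% | 2.02 | 3.84 | 3.86 |
| 4.0 | 35% / 25% | 38% / 85% | 63% / 91% | 2.37 | 3.41 | 3.88 |
| 2.0 | 58% / 35% | 52% / 76% | 85% / 88% | 1.15 | 2.36 | 1.88 |
| 1.0 | 53% / 53% | 38% / 38% | 75% / 75% | 1.01 | 1.04 | 1.04 |

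In the second row a 47-point difference (85 − 38) is recorded as 15 points (90 − 75). With no drug effect and equal rescue, all three rules give about 1.0.

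Censoring at SoC comes close to the true HR because, within each arm, the simulation makes the intention to use rescue independent of the attack's own course. In the trial SoC goes to attacks that are doing badly, so that censoring would be informative.

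**The case against.** - **The protocol is silent; it has not chosen.** It defers detail to a Study 202 SAP, due before database lock and not among the documents. That SAP may contain a rule. This stands as a limit on certainty. It does not remove the point, because the definitions followed literally do credit post-SoC relief. Section 9.3.1 also lets the project statistician and sponsor staff be unblinded once the 12th Part 1 subject completes, so a rule first written near lock could be written with knowledge of the data.
- **Using data after rescue is a legitimate treatment-policy strategy.** True. The defect is that no strategy is stated for these endpoints, while the 4-hour responder endpoint follows a different one.
- **The study is exploratory.** Section 13.1 says the sample size has no statistical basis. The one stated hypothesis (13.2) concerns the 4-hour VAS responder endpoint, which has an explicit rescue rule. Differential rescue is measured directly through SoC use and time to SoC. Under the mechanism described, the bias is toward no difference, so it does not manufacture efficacy. All of this stands and limits the severity.
- **The remedy has its own bias.** Counting SoC as no relief gave HRs of 3.41 to 5.24 against a true 4.0, and 2.36 against 2.0, because it combines the decision to rescue with relief. This stands, and it is why the strategy must be named and accompanied by sensitivity analyses.

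**Conclusion.** The gap is real and should be fixed. Sections 7.2.1 and 13.3.3 give no rule for SoC in the five time-to-relief endpoints or in VAS change at any post-dose time point, and as written relief after SoC counts for the blinded treatment. The contrast is attenuated if the drug works and placebo attacks are therefore rescued more often. Every size above rests on assumed relief and rescue rates: under them, true HRs of 2.0 to 4.0 were recorded as 1.15 to 2.37.

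A reader might infer more than the documents support:

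- *That the drug effect is hidden or the order reversed.* No simulated HR crossed 1. A negative difference (−2 points) appeared only in 24-hour proportions, with 25% and 50% relief without rescue and 90% relief after rescue, and proportions ignore when relief occurs.
- *That efficacy as a whole is compromised.* The 4-hour VAS responder endpoint, SoC use and time to SoC are not affected. Time to stable or improved VAS may be affected less, since it can often occur before 4 hours.
- *That the dose comparison is flattened.* Section 13.3.3 specifies no between-dose analysis of time to relief, and none was computed here.

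**What to change.** In Protocol 7.2.1 and 13.3.3 and in the Study 202 SAP, before any unblinded analysis:

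1. **Time-to-relief endpoints, main analysis.** Extend the existing rescue-is-failure rule: an attack that uses SoC before the event is counted as not relieved and censored at 24 hours. State that this is a composite strategy, estimating relief without rescue.
2. **Sensitivity analyses.** (a) Ignore SoC; (b) censor at SoC, noting that such censoring is informative.
3. **VAS change, every post-dose time point at which SoC has already been used, including 1 to 4 hours.** State the strategy, and report a supplementary analysis that does not credit post-SoC values to study drug. Carrying forward the last pre-SoC value should not be the main method. An attack rescued before the 1-hour entry would carry its baseline forward, a change of 0, which 7.2.1 classes as stable although the 4-hour rule calls the same attack a failure.

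The cost is a few sentences and one derivation, since the diary already records SoC through 24 hours. The downside is lower absolute relief rates and an estimand that combines rescue behaviour with relief. When subjects may take SoC does not change.

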#### 7.2.2. Safety Endpoints

Safety endpoints will include the number and proportion of subjects who: discontinue due to a treatment-emergent AE; experience a treatment-emergent SAE; experience a Grade 3 or 4 treatment-emergent AE; and experience a treatment emergent Grade 3 or 4 laboratory abnormality.

BioCryst Pharmaceuticals, Inc. CONFIDENTIAL

Protocol BCX7353-202 Version 4.0

BCX7353

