#### **Duration of treatment:**

Participating subjects will receive 3 single oral doses of study drug to treat an HAE attack approved for study drug treatment: 2 doses of BCX7353 and 1 dose of placebo.

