#### **Statistical methods:**

Due to the exploratory nature of this study, no formal power or sample size calculations were used to determine sample size. Descriptive statistics for disposition, demographics, and baseline characteristics will be presented by treatment sequence. All analyses of efficacy and safety will be attributed to the treatment assignment at the time of the assessment.

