## 9. TREATMENT OF SUBJECTS

# 9.1. Description of Study Drug

The study drug or IMP in this study consists of BCX7353 powder and matching placebo powder for reconstitution as oral solutions. Subjects will be randomized to 1 of 3 treatment sequences and will receive 2 single doses of BCX7353 and 1 single dose of matching placebo:

- Two single oral doses of BCX7353 750 mg and one oral dose of matching placebo (Part 1)
- Two single oral doses of BCX7353 500 mg and one oral dose of matching placebo (Part 2)
- Two single oral doses of BCX7353 250 mg and one oral dose of matching placebo (Part 3)

The active ingredient for this study is BCX7353. All clinical doses of BCX7353 provided in this protocol are in reference to the hydrochloride (HCl) salt. BCX7353 is a white to tan powder. The IMP is formulated as a single unit dose drug in a bottle formulation that will be reconstituted with an oral vehicle prior to dosing. The oral vehicle to be used for reconstitution is a SyrPalta: Sterile Water for Irrigation solution and is supplied with the IMP.

The taste-masked placebo for this study is lactose monohydrate which is an off-white powder. The IMP is formulated as a single unit dose drug in a bottle formulation that will be reconstituted with an oral vehicle prior to dosing. The oral vehicle to be used for reconstitution is a SyrPalta, Sterile Water for Irrigation and Bitrex® 0.256%w/v (50ppm) solution and is supplied with the IMP.

Quotient Clinical (Nottingham, UK) will manufacture the IMP.

Additional details for the chemical and physical characteristics of BCX7353 may be found in the IB.

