# 13.3.1.1. Full Analysis Set

The Full Analysis Set (FAS) population will include all subjects/subject attacks treated. Subjects/subject attacks will be analyzed according to the treatment randomized. The FAS population will be the primary population for efficacy analyses.

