## 13.3.1.2. Safety Population

The safety population will include all subjects who received at least 1 dose of study drug. Subjects will be analyzed according to the treatment received. This population will be used for all analyses of accountability, demographics, and safety.

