## 13.3.4. Analysis of Safety Variables

Adverse events will be mapped to a Medical Dictionary for Regulatory Activities (MedDRA) preferred term and system organ classification. Any event reported on the subject's study record that occurs on or after the initiation of study drug within a given treatment period is defined as treatment emergent. Additionally, it is assumed that an AE that is reported to have started on the day of subject dosing to treat an attack without an associated onset time may have occurred after the initiation of study drug. Hence, AEs occurring on the day of subject dosing to treat an attack with no associated onset time will be assumed to be treatment emergent. AEs will be attributed to the corresponding treatment assignment of the corresponding treatment period. The occurrence of treatment-emergent AEs will be summarized by treatment group using MedDRA preferred terms, system organ classifications, and severity. Separate summaries of treatment-

emergent SAEs and AEs considered to be related to study drug will be generated. All AEs will be listed for individual subjects showing both verbatim and preferred terms.

Descriptive summaries of vital signs, weight, ECG parameters, and clinical laboratory results will be presented separately for each treatment group. Laboratory abnormalities will be graded according to the DMID Adult Toxicity Table (Publish Date: Draft, November 2007, see Appendix 15.1). Any graded abnormality that occurs following the initiation of study drug and represents at least 1-grade increase from the baseline assessment for a given treatment period is defined as treatment emergent. The number and percentage of subjects experiencing treatment-emergent graded toxicities will be summarized by treatment group. Laboratory toxicity shifts from baseline to post-baseline assessments will be summarized by treatment group.

Clinically significant abnormal morphological ECG findings will be summarized by treatment group.

Physical examination results will be presented in listings.

Concomitant medications will be coded using the World Health Organization (WHO) dictionary. These data will be summarized by treatment group.

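### Graded laboratory toxicities are shown as percentages of subjects by treatment, but each subject takes two active doses and one placebo dose, and the protocol states no per-dose safety denominator

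*Protocol*

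**What the plan says.** Dosing is two to one within each subject. The synopsis gives "2 doses of BCX7353 and 1 dose of placebo" per subject, and Protocol section 9.1 repeats that subjects "will receive 2 single doses of BCX7353 and 1 single dose of matching placebo". All three sequences (ABA, BAA, AAB) have this composition.

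The unit for safety is the subject. Section 7.2.2 reads: "Safety endpoints will include the number and proportion of subjects who: discontinue due to a treatment-emergent AE". It goes on to serious adverse events, Grade 3 or 4 adverse events and Grade 3 or 4 laboratory abnormalities. The safety population (13.3.1.2) is also made up of subjects: "Subjects will be analyzed according to the treatment received".

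Events go to the treatment of the period. Section 13.3.4 says "AEs will be attributed to the corresponding treatment assignment of the corresponding treatment period", and the synopsis says "All analyses of efficacy and safety will be attributed to the treatment assignment at the time of the assessment".

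One display is fully specified. For laboratory toxicities, section 13.3.4 says: "The number and percentage of subjects experiencing treatment-emergent graded toxicities will be summarized by treatment group". For adverse events the same section promises summaries of their occurrence by treatment group and does not say whether events, subjects or periods are counted.

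Efficacy is handled differently. The Full Analysis Set (13.3.1.1) allows an attack-level unit ("Subjects/subject attacks will be analyzed according to the treatment randomized"), and the binary efficacy endpoints in 7.2.1 are proportions of attacks. The protocol gives no matching per-dose, per-attack or exposure-based denominator for safety.

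**The concern.** A subject enters the active column if an event follows either of two doses, but enters the placebo column only if it follows the single placebo dose. Laboratory samples are taken at all three post-attack visits (section 10.3.4), so two sets follow active drug and one follows placebo. The two percentages therefore rest on unequal exposure, and the active figure is expected to be higher even if the drug does nothing.

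Safety and tolerability is a secondary objective, and the by-treatment tables are where a reader will compare each dose with placebo. Parts have at most 36 or 12 subjects, so a handful of events shapes the impression. A near-doubled percentage could be taken for a drug signal when planning later studies.

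**Working it through.** The documents give no figure for this contrast and no event rate for safety, so there is nothing to reproduce. The check asks what the display would show for an inert drug.

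**Inputs from the protocol:** two active doses and one placebo dose per subject (synopsis, 9.1); up to 36 subjects in Part 1 and up to 12 in each of Parts 2 and 3 (8.1); sequences ABA, BAA and AAB in a 1:1:1 ratio (7.1).

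**Assumptions:** a risk p of an event after any one dose, the same for drug and placebo, taken as 1% and 5%; a within-subject correlation rho between doses, taken as 0, 0.5 and 1.

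**Formula.** The placebo proportion of subjects is p. The active proportion is the chance of at least one event in two doses, 2p − [p² + rho·p(1−p)]. Dividing by p gives the ratio 2 − p − rho(1−p).

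- p = 1%: 2 − 0.01 = 1.99 at rho 0; 1.99 − 0.5 × 0.99 = 1.495 at rho 0.5; 1.00 at rho 1.
- p = 5%: 2 − 0.05 = 1.95 at rho 0; 1.95 − 0.5 × 0.95 = 1.475 at rho 0.5; 1.00 at rho 1.

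**Expected subjects with an event, rho 0 (active vs placebo):**

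- Part 1, n = 36: 0.72 vs 0.36 at 1% (gap about 0.4); 3.51 vs 1.80 at 5% (gap 1.7).
- Part 2 or 3, n = 12: 0.24 vs 0.12 at 1%; 1.17 vs 0.60 at 5%.
- At rho 0.5 the Part 1 gaps fall to 0.18 (0.54 vs 0.36) and 0.86 (2.66 vs 1.80).

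**Discontinuation for an adverse event.** This can happen only once per subject, and section 10.3.5 treats a discontinuation as early only if it precedes treatment of the third attack. I therefore count it after dose 1 or dose 2 only. With q = 1 − p and averaging over the three sequences:

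- Active discontinuations: 2p(1+q)/3. Subjects exposed to active: (2+q)/3.
- Placebo discontinuations: p(1+q)/3. Subjects exposed to placebo: (1+q+q²)/3.
- At p = 5%: 0.0650/0.9833 = 6.6% vs 0.0325/0.9508 = 3.4%, ratio 1.93. At p = 1% the ratio is 1.99.

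**How often the table would lean one way.** Exact binomial, Part 1, rho 0, inert drug. The first figure is the probability that active exceeds placebo, the second that it falls below:

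- Subject counts: 71% and 15% at p = 5%; 40% and 17% at p = 1%.
- Events per dose given: 46% and 42% at p = 5%; 37% and 26% at p = 1%.

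**With doses as the denominator.** If all 36 subjects complete Part 1, there are 72 active and 36 placebo doses. The expected proportion is p in both columns for any rho, so the ratio is 1.00. For discontinuation per dose given the ratio is also 1.00.

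**The case against.** The best counter-argument is that table denominators belong in the analysis plan. Section 13.3 defers endpoints and populations to a SAP, and the SAP supplied here is for Study BCX7353-302, a parallel-group daily-dosing trial. Its rates per 100 person-years do not apply to this study. Study 202's own plan may already have a per-dose row. That limits the point to what the protocol states, but it does not undo the laboratory rule, which the protocol spells out.

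A reader might infer that the protocol commits to subject percentages by treatment for every safety endpoint. It does not. Section 7.2.2 never says by treatment, and 13.3.4 leaves the unit for adverse events open. For serious events, Grade 3 or 4 adverse events and discontinuations, the display is an inference from 7.2.2, 13.3.1.2 and 13.3.4 taken together.

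It can also be said that subject incidence is a legitimate quantity: the risk over a two-dose course. That stands. Section 5.4.4.2 says it is not known whether repeated single doses lead to hypersensitivity, and a pooled per-dose rate would dilute an effect that appears only on re-exposure. The subject count should therefore stay, and the per-dose figures should be split by first and second active dose.

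Finally, the consequences are limited. No safety test is planned. The triggers in section 12.2 for convening the data monitoring committee count affected subjects and do not use a drug-placebo contrast. Laboratory summaries by visit and treatment, as the synopsis describes them, carry one dose per subject per visit. Comparisons between active doses are balanced at two doses each. All adverse events are listed by subject. All of this stands.

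**Conclusion.** The point holds as a minor one. Following the stated laboratory display, an inert drug is expected to show a higher percentage of subjects with an event than placebo unless events are perfectly correlated within subjects. The direction follows from the two-to-one dosing; the size depends on the assumed p and rho. A ratio close to 2 should be read as the independent-periods case, not as a property of the trial.

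Two stronger readings are not supported. One is that the drug column would show a higher event rate: the lean is in subjects with an event, and the rate per dose is unaffected. The other is that safety conclusions are compromised: the absolute gaps are under two subjects in Part 1 at the risks examined, the contrast is descriptive, and the lean overstates harm.

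**What to change.** In section 13.3.4, or in Study 202's own SAP, keep the subject counts and add, for each treatment, the number of doses (treated attacks) followed by an event over the number of doses given. Show the active results for the first and second active dose separately as well as pooled. State for each adverse event table whether it counts events, doses or subjects.

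The cost is a few extra counts and percentages per table. Attribution by treatment period already supplies what is needed, so no new data are collected and nothing in the conduct of the trial changes.
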